#### **5.4.2.1 Mini Mental State Examination (MMSE)**

The MMSE is a set of standardized questions used to evaluate possible cognitive impairment and help stage the severity level of this impairment (Folstein et al. 1975). The questions target six areas: orientation, registration, attention, short-term recall, language, and constructional praxis/visuospatial abilities. The MMSE is a participant-based assessment. The score ranges from 0-30, with lower values indicating a greater impairment.

#### **5.4.2.2 Digit Symbol Substitution Test (DSST)**

Coding, also called Digit Symbol Substitution Test (or DSST), is a subtest from the Wechsler Adult Intelligence Scale-Fourth Edition (WAIS-IV; Wechsler 2008). Coding is a participant-based assessment that measures speed of processing and associative

memory. The test is known to be sensitive to disease progression (Lezak et al. 2004). The 120-second version of the test will be used in this study.

### **5.4.2.3 Verbal Fluency Task**

The category verbal fluency (e.g., animals) is a participant-based assessment that measures speed and flexibility of verbal thought. Verbal fluency tests are sensitive tools for detecting dementia (Pasquier et al. 1995; Lezak et al. 2004) and for monitoring decline over time (Clark et al. 2009).

### **5.4.2.4 Alzheimer’s Disease Cooperative Study, Activities of Daily Living Scale (ADCS-ADL), Instrumental Score**

The ADCS-ADL instrumental score is a sub score of the ADCS-ADL scale, see Section 5.4.1.2. The ADCS-ADL instrumental score used in this study is the sum of items 6a and 7 to 23.

### **5.4.3 COVID-19 Related Sensitivity Analyses for Secondary Endpoints**

During the COVID-19 pandemic, many countries took movements’ restriction policy. Among the clinical outcomes collected in the study, some questionnaires may be particularly impacted. These questionnaires include items describing actions that are strongly constrained or prohibited by restriction policies.

We define modified versions of the total score for these scales. These modified scales scores may be used to perform sensitivity analysis aiming at understanding and mitigating the impact of the COVID-19 pandemic on study results and interpretation, in line with the primary clinical question of interest.

#### **5.4.3.1 ADCS-ADL COVID-19 Modified Total Score**

The original ADCS-ADL is a 23 item scale with a total score range of 0-78. The following items were identified as being particularly impacted by the pandemic related restrictions:

- Item 2: Optimal walking performance, maximum 3 points
- Item 15: Optimal performance getting around/travelling outside the home, maximum 4 points
- Item 16a/b: Shopping trips - selecting items and paying without supervision, maximum 4 points
- Item 18: Left away from home, maximum 3 point

A sensitivity analysis may be conducted, using a modified version of the ADCS-ADL total score after removing of these four items, resulting in a 19-item scale with a score range of 0-64. This alternative version will be referred to as “ADCS-ADL COVID-19 modified total score”.

### 5.4.3.2 FAQ COVID-19 Modified Total Score

The original FAQ is a 10-item scale with a score range of 0-30. The following items were identified as being particularly impacted by the pandemic related restrictions:

- Item 3: Shopping alone, maximum 3 points
- Item 10: Travelling outside of the neighborhood, maximum 3 points

A sensitivity analysis may be conducted, using a modified version of the FAQ total score after removing of these 2 items, resulting in an 8-item scale with a score range of 0-24. This alternative version will be referred to as “FAQ COVID-19 modified total score”.

## 5.5 EXPLORATORY ENDPOINT(S) ANALYSIS

The same primary estimand’s analysis strategy (see Section 5.3.2) will be applied to continuous exploratory endpoints listed in Table 6, with the following exceptions for the corresponding estimator:

- *the imputation model will not include, as covariates, the baseline ADAS-Cog 13 total score and the baseline ADCS-ADL total score*

*The imputation model will thus include treatment group, visit, and treatment-by-visit interaction, the baseline score and the baseline score-by-visit interaction, and the randomization stratification factors, namely: disease stage, geographic region, the use of AD medication at baseline and the APOE ε4 status*

- *the analysis model will not include, as covariates, the baseline ADAS-Cog 13 total score and the baseline ADCS-ADL total score*

*The analysis model will thus include treatment, the baseline score and the randomization stratification factors, namely: disease stage, geographic region, the use of AD medication at baseline and the APOE ε4 status*

. For all continuous exploratory endpoints, the ANCOVA analysis model will include the baseline score of the exploratory endpoint, the disease stage, geographic region, the use of AD medication at baseline and the APOE ε4 status as covariates.

For ordinal endpoints, only descriptive analyses will be considered, summarizing the frequencies of the different categories, as well the proportion of participants with a certain shift in categories.

The Resource Utilization in Dementia Scale–Lite (RUD-Lite) and the EuroQoL–5 Dimensions (EQ-5D-5L) scales will be used in this study for informing pharmacoeconomic evaluations and will be reported separately.

**Table 6 Exploratory Endpoints**

Exploratory Efficacy Endpoint	Type
Clinical Dementia Rating-Global Score (CDR-GS)	Ordinal
CDR-Individual Components	Continuous
Dependency Level, as assessed by the Alzheimer disease cooperative study - activities of daily living (ADCS-ADL) score	Ordinal
Integrated AD Rating Scale (iADRS)	Continuous
Quality of Life–Alzheimer’s Disease (QoL-AD)	Continuous
Neuropsychiatric Inventory Questionnaire (NPI-Q)	Continuous
Zarit Caregiver Interview–Alzheimer’s Disease (ZCI-AD)	Continuous

ADCS-ADL = Alzheimer disease cooperative study-activities of daily living; ADCOMS = AD Composite Score; CDR-GS =Clinical Dementia Rating-Global Score; EQ-5D= EuroQoL–5 Dimensions; iADRS = Integrated AD Rating Scale; NPI-Q= Neuropsychiatric Inventory Questionnaire ; QoL-AD =Quality of Life–Alzheimer’s Disease; ZCI-AD=Zarit Caregiver Interview–Alzheimer’s Disease.

### **5.5.1 Clinical Dementia Rating–Global Score (CDR-GS) and Individual Components of the CDR scale**

The Washington University CDR is a global assessment instrument that yields global scores (GS) and sum of boxes (SOB) scores. The CDR is derived from a semi-structured interview with the participant and an appropriate informant, and it rates impairment in six categories (Memory, Orientation, Judgment and Problem Solving, Community Affairs, Home and Hobbies, and Personal Care) on a 5-point scale for which 0 = no impairment, 0.5 = questionable impairment, and 1, 2, and 3 = mild, moderate, and severe impairment, respectively. From the six individual category ratings, or box scores, the CDR-GS is established by clinical scoring rules, for which CDR 0 = no dementia and CDR 0.5, 1, 2, or 3 = questionable, mild, moderate, or severe dementia, respectively (Morris 1993).

### **5.5.2 Dependence Level Assessed by the ADCS-ADL Score**

To calculate dependence levels, scores on the ADCS-ADL can be transformed into discrete levels of disability via an algorithm developed initially by Kahle-Wroblewski (2015). Items from the ADSC-ADL were mapped to 6 levels of dependence derived from the Dependence Scale (Zhu et al., 2009), ranging from Level 0: no impairment in instrumental or basic ADLs to Level 5: complete incontinence or inability to transfer. Four subscales were used to aid the construction of dependence levels, including bADLs, domestic/household activities, communication/engagement and outside

activities. The mapping of items to dependence levels was validated using additional clinical and economic measures.

A revised algorithm, developed to a) remove ambiguity regarding the contribution of some items and b) add clarity on the handling of missing data, will be used to calculate the dependence levels. Progression to greater levels of dependence is indicative of disease progression and is informative for a variety of care providers and stakeholders. This algorithm is provided in appendix, see [Appendix 2](#).

### **5.5.3 Integrated AD Rating Scale (iADRS)**

The iADRS is a composite of cognition and function that combines scores from the ADAS-Cog-13 (cognition) and the instrumental component of the ADCS-ADL (function) ([Wessels et al., 2018](#)). A sum score of the total scores of both components is calculated (ADAS-Cog is reversed) using the following formula:

$$iADRS = [-(ADAS-Cog13) + 85] + ADCS-iADL.$$

Total score range from 0 to 141. The iADRS total score will be generated and results may be reported in the CSR.

### **5.5.4 AD Composite Score (ADCOMS)**

The ADCOMS was developed to assess cognition and function in early stages of AD. It is a composite score that combines 12 items from existing AD measures, specifically the ADAS-Cog (Delayed word recall, Orientation, Word recognition, Word finding difficulty), MMSE (Orientation time and Constructional praxis) and all CDR-SB items ([Wang et al., 2016](#)). The ADCOMS score was built using a linear longitudinal model to characterize the relationship between disease progression and the individual items from existing AD clinical scales. A PLS regression procedure was used to identify individual clinical scale items that represent AD-related clinical decline over time to calculate their respective weighting factors. The resulting composite ADCOMS score is a weighted linear combination of the individual scale items selected in the fitted PLS model. Items with small contribution to the PLS model were removed according to Wold's criterion (a Variable Importance of Projection below 0.8). Total score range from 0 to 1.97, with lower scores indicating greater impairment. The ADCOMS total score will be generated and results may be reported in the CSR.

### **5.5.5 Quality of Life–Alzheimer’s Disease (QoL-AD)**

The Quality of Life–Alzheimer’s Disease (QoL-AD) was developed to assess quality of life (QoL) in participants who have dementia ([Logsdon et al. 1999](#), [Logsdon et al 2002](#)). The QoL-AD consists of 13 items covering aspects of participants’ relationships with friends and family, physical condition, mood, concerns about finances, and overall assessment of QoL. The total score is the sum of the 13 items and ranges from 13 to 52, with higher scores indicating better health-related QoL. In this study, the QoL-AD

will be administered in a standardized, structured interview format to participants by investigative staff in order to gather participant responses about QoL. The study partner will also complete the study partner version of the questionnaire to enable proxy responses from the study partner.

### **5.5.6 Neuropsychiatric Inventory Questionnaire**

The Neuropsychiatric Inventory-Questionnaire (NPI-Q) ([Kaufer et al. 2000](#)) was developed to assess a wide range of behaviors encountered in dementia participants, to provide a means of distinguishing severity of behavioral changes, and to facilitate rapid behavioral assessment through the use of screening questions. It is an informant-based instrument in which 12 behavioral domains are evaluated. The recall period is the past month, and severity scores range from 0 to 36, with higher scores indicating greater severity. The study partner's distress portion of the scale was not used in this study.

### **5.5.7 Zarit Caregiver Interview–Alzheimer's Disease (ZCI-AD)**

The Zarit Caregiver Interview-Alzheimer's Disease (ZCI-AD) is a modified version of the Zarit Burden Interview 22-item version, which was originally designed to reflect the stresses experienced by caregivers for people with dementia ([Zarit and Zarit 1990](#)). The modified version includes modifications in item and title wording (e.g., removal of "your relative" to refer directly to the participant, removal of "burden" from title), inclusion of additional items, the use of 11-point numerical rating scales for each item and a 4 week recall period. The ZCI-AD measure consists of 27 items covering 13 domains (i.e., humanistic impact domain (14 items) including the domains physical (3 items), emotional (4 items), social (3 items), and daily life (4 items), and the additional domains exhaustion (2 items), dependence (2 items), worry (2 items), role perception (3 items), financial impact (1 item), difficulty with medication (1 item), overall difficulty of caregiving (1 item), and sadness (1 item)). The ZCI-AD is completed by the study partner without involvement from the site staff. The ZCI-AD is scored on a domain level with each domain score ranging from 0 to 100 with higher scores indicating higher level of impact. All item responses are re-coded on a 0 to 4 scale (response category 0=0; response category 1,2, and 3=1; response category 4,5,and 6=2; response category 7 and 8=3; response category 9 and 10=4) and items of a domain are summed up and transformed to 0 to 100 score range. Domain scores are only calculated if responses of at least 80% of items of the respective domain are available. The ZCI-AD has been validated in prodromal, mild and moderate stages of AD ([Bernards, C et al.](#))

## **5.6 SAFETY ANALYSES**

Descriptive statistics will be used to analyze all safety data collected in the double-blind treatment period in the safety-evaluable analysis set, unless otherwise specified.

Safety data collected from the day of the first dose of blinded study drug up to 14 weeks after the last dose of blinded study drug (but no later than the day before the first OLE dose for the participants who entered the OLE period) will be included in the

beyond the 14-week post last dose period and until the end of the study will be included in the follow-up period analyses.

For participants who entered the OLE period, safety data collected from the day of the first OLE dose up to 14 weeks after the last OLE dose will be included in the OLE period analyses

Safety analyses will be assessed through summaries of exposure to study treatment, adverse events, changes in laboratory test results (including shift tables), MRI findings, changes in vital signs and ECGs, and changes in C-SSRS scores.

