3.3.5.1 Rationale for Duration of Study Follow-Up (14 Weeks)

The primary purpose of the 14-week follow-up visit (i.e., 14 weeks after the last dose) is to evaluate the long-term safety of gantenerumab. The apparent terminal half-life of gantenerumab is in the order of 24 days, and gantenerumab is cleared from plasma after approximately 16 weeks (approximately 5 half-lives). Therefore, safety assessments performed 14 weeks after the last dose are considered sufficient to evaluate residual effects on peripheral safety outcomes. In addition, efficacy assessments at the follow-up visit may support an enduring effect of gantenerumab after treatment is stopped.

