4.6.7 Follow-Up Assessments

Participants who complete the double-blind treatment period and who are not willing to enroll in an OLE or these who complete the OLE period (defined as administration of at least three 510-mg doses Q4W) and are not willing to enroll in the WN42171 open-label study will be asked to return to the clinic 14 weeks and 50 weeks after the last dose of study drug for the follow-up visits (Follow Up 1 and Follow Up 2 or OLE Follow Up 1 and OLE Follow Up 2, respectively)..

When participants complete the treatment period or discontinue early, every effort should be made to ensure that the safety follow-up period and all related assessments are completed.

After the study completion or early termination visit, adverse events should be followed as outlined in Sections [5.5](#) and [5.7](#). Refer to the schedule of activities (see [Appendix 1](#)) for the list of assessments to be performed at the follow-up visits.

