Appendix 1: Schedule of Activities (cont.)

Table 3: Scenario 1 / Week 104 to the End of Study: 510 mg Q2W (3-Month Extension)

ADAS-Cog13=Alzheimer's Disease Assessment Scale–Cognition, Subscale 13; ADCS-ADL =Alzheimer Disease Cooperative Study Group–Activities of Daily Living; CDR =Clinical Dementia Rating; CSF =cerebral spinal fluid; C-SSRS=Columbia–Suicide Severity Rating Scale; DTI=diffusion tensor imaging; EQ-5D =EuroQoL-Five Dimensions; FAQ =Functional Activities Questionnaire; FCSRT=Free and Cued Selective Reminding Test; MMSE =Mini-Mental State Examination; MRI =magnetic resonance imaging; NPI-Q =Neuropsychiatric Inventory–Questionnaire; OLE=open-label extension; PET =positron emission tomography; PK =pharmacokinetic; Q2W =every 2 weeks; QoL-AD =Quality of Life–Alzheimer's Disease; RBR =Research Biosample Repository; RUD-Lite =Resource Utilization in Dementia–Lite; SC =subcutaneous; Unsched =unscheduled; Wk =week; ZCI-AD =Zarit Caregiver Interview–Alzheimer's Disease.

B =before study drug administration; P =participant completion; P&SP=participant and study partner completion; SP=study partner.

Notes: The visit window is ± 3 days for dosing days and ± 3 days for Week 115 non-dosing days. For Q2W injections, the recommendation is not to administer more than 1020 mg (i.e., 2 times 510 mg Q2W) within 28 days. Participants should return to initial planned schedule per randomization for subsequent visits.

SoA from Week –12 to Week 103 for scenario 1 is described in [Appendix 1, Table 1](#) and [Table 2](#).

- ^a Visit may be split over 2 consecutive days. All cognitive and functional assessments should be completed first. All safety assessments (e.g., vitals, blood tests, and ECGs) should be completed on the day of dosing. Whenever possible, cognitive and functional assessments should be performed at the visit timepoints stipulated in the schedule of activities. However, in exceptional circumstances, if the caregiver, the primary rater, or even the participant cannot perform these assessments as per schedule of activities, they may be performed up to 4 weeks out of window.
- ^b Transition to OLE study for participants who are eligible to participate.
- ^c Visit suitable for home administration of gantenerumab.

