**Figure 1 Overall Study Design**

Each study consists of three distinct periods:

**Screening** (including an optional prescreening): The screening period may last up to 12 weeks for each eligible participant.

**Double-blind treatment period:** After screening, participants who meet all eligibility criteria will be randomly assigned to one of two arms (active drug or placebo) in a 1:1 ratio. Following baseline assessments, each participant will receive a minimum of 9 subcutaneous (SC) administrations every 4 weeks (Q4W) of study drug (uptitration period), followed by up to 40 administrations every 2 weeks (Q2W) of study drug at target dose in the double-blind treatment period. The last dose of study drug will be administered at Week 114. At the end of the double-blind treatment period, 2 weeks after the last dose, all participants will undergo the final efficacy and safety study visit. Participants who have already completed the double-blind treatment period prior to implementation of Protocol Version 4 will have received up to 34 SC Q2W administrations of study drug during the double-blind treatment period. The last dose will have been administered at Week 102, and their final efficacy and safety visit will be at Week 104.

The Sponsor will emphasize to Investigators the importance of collecting data for the primary endpoint through Week 116, even if participants withdraw from treatment but do not withdraw from the study.

**Post-double-blind treatment period:** After the final efficacy and safety study visit for the double-blind treatment period, all participants will be asked to come back for the long-term follow-up visits or to continue in the open-label extension (OLE). Participants will either directly enter the separate WN42171 (hereafter referred to as “POSTGRADUATE”) OLE study or enter a parent study OLE period. If entering the parent study OLE period, they will be required to complete the uptitration period (a minimum 36 weeks) following which they will then be able to roll over to the

POSTGRADUATE OLE study. This second option is for participants at sites where POSTGRADUATE is not yet approved when they have reached the end of the double-blind treatment period.

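### SAP 5.6 ends the double-blind safety period on the day the 14-week follow-up visit falls due, so a one-day difference splits that visit's laboratory, ECG and vital-sign results between two summaries

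*SAP*

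**What the plan says.** SAP 5.6 assigns safety data to periods by time since the last dose. The double-blind period runs from the first blinded dose "up to 14 weeks after the last dose of blinded study drug". The SAP sets one cap on this: "but no later than the day before the first OLE dose for the participants who entered the OLE period". Data "beyond the 14-week post last dose period and until the end of the study will be included in the follow-up period analyses". The OLE period is closed in the same way, 14 weeks after the last OLE dose.

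Protocol 4.6.7 says that participants who complete double-blind treatment and do not enrol in an OLE "will be asked to return to the clinic 14 weeks and 50 weeks after the last dose of study drug for the follow-up visits". Protocol 3.3.5 extends these assessments to participants who stop treatment early, and Protocol 4.1.3 bars those participants from the OLE. Protocol 3.3.5.1 gives the visit a safety purpose.

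In Protocol Appendix 1, Table 3, the first follow-up visit is at Week 128. It includes ECG, chemistry and haematology, weight, vital signs and adverse events, but no scheduled MRI or C-SSRS. The table notes give a 3-day window for dosing days and 3 "days for Week 115 non-dosing days". They give none for the follow-up visits.

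SAP 5.6.4 to 5.6.6 summarise laboratory, vital-sign and ECG data by assessment visit. The SAP sets analysis windows for clinical scales, PET, CSF, plasma biomarkers and volumetric MRI (Tables 4, 7, 9, 10, 11 and 12), but none for these safety assessments.

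**The concern.** A cut placed on a visit's due date leaves no room for ordinary scheduling variation. Two participants seen one day apart at the same scheduled visit would have their results reported in different periods. Because these results are summarised by visit, the 14-week visit would appear in both sets of tables, each time with part of its participants. Neither table would describe the visit, and its denominators would depend on attendance dates. This is the visit that the protocol relies on to look for residual effects after treatment stops, and those attending include participants who discontinued early, some of them for safety reasons.

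**Working it through.** **Inputs**
- Last scheduled double-blind dose: "The last dose of study drug will be administered at Week 114" (SAP 1.2, text under Figure 1).
- First follow-up visit: 14 weeks after the last dose (Protocol 4.6.7), labelled Week 128 (Protocol Appendix 1, Table 3).
- End of the double-blind safety period: 14 weeks after the last dose (SAP 5.6).

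**Step 1: reproduce the scheduled visit.** 114 + 14 = 128, which matches Table 3. The other schedules agree: 102 + 14 = 116 (Table 2) and 126 + 14 = 140 (Table 4).

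**Step 2: convert to study days.** With Day 1 as the first dose, Week w is Day 7w + 1.
- Week 114: 7 × 114 + 1 = Day 799.
- Week 128: 7 × 128 + 1 = Day 897.
- Gap: 897 − 799 = 98 days.
- The cut: 14 × 7 = 98 days.

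The due date and the cut are the same day.

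**Step 3: apply the rule.** Let f be the number of days by which the visit is early (negative) or late (positive). The visit falls 98 + f days after the last dose, and it is in the double-blind period only if 98 + f ≤ 98, that is, f ≤ 0. A visit on day 98 is in; a visit on day 99 is out.

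**Step 4: share of visits moved.** The documents give neither a window nor a distribution of dates for this visit, so the following are assumptions. If f is equally likely to be any whole day from −k to +k, the share moved is k / (2k + 1).

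| Assumed spread of f | Moved to follow-up |
|---|---|
| −3 to +3 days | 3/7 = 43% |
| −7 to +7 days | 7/15 = 47% |
| 0 to +3 days (never early) | 3/4 = 75% |
| never late | 0 |

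The existence of the split does not depend on this table; only its size does.

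**Step 5: compare with another cut in the same SAP.** For amyloid PET after early discontinuation (SAP 5.7.5.3), the expected visit is 14 days after the last dose. The SAP adds the 42-day visit window and cuts at 14 + 42 = 56 days. SAP 5.6 uses the due date with nothing added.

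**The case against.** The strongest case on the other side has four parts.

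- **The rule may be incomplete as read.** In the copy reviewed, the SAP 5.6 sentence breaks off and resumes partway through the follow-up rule, so the lost words could hold a visit rule. SAP 1 also leaves dataset details to Data Analysis Plan Modules 2 and 3, which are not available here. This stands as a limit on certainty. Even so, both readable halves use 14 weeks without a margin, and the definition of an analysis period belongs in the SAP.
- **An on-time visit is not excluded.** A reader might infer that the 3-day dosing window alone pushes visits held on their planned Week 128 date out of the period. The documents do not establish this. Protocol 4.6.7 times the visit from the last dose, and Week 128 is the label that follows from a Week 114 dose. The split therefore needs a visit that is late relative to the actual last dose.
- **The consequence is small.** Safety analyses are descriptive and the rule is identical in both arms. Late results are still reported, in the follow-up analyses. All of this stands.
- **Fourteen weeks was a deliberate choice.** A reader might argue for a longer adverse-event period because the protocol states that "gantenerumab is cleared from plasma after approximately 16 weeks (approximately 5 half-lives"). The same section goes on to conclude that "safety assessments performed 14 weeks after the last dose are considered sufficient to evaluate residual effects on peripheral safety outcomes". The sponsor weighed both figures, so extending adverse-event time to 16 weeks would be a preference with a trade-off and does not correct an error.

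**Conclusion.** The point holds as a minor defect in a stated rule. As written, SAP 5.6 divides one scheduled visit between two descriptive summaries on a one-day difference. It affects participants who attend a 14-week follow-up visit, namely completers who do not enter an OLE and those who stop treatment early. OLE entrants are cut at the day before the first OLE dose. The data affected are those dated by the visit: laboratory, ECG and vital-sign results.

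The size cannot be fixed from the documents. About 43% to 47% of such visits would move if dates varied evenly by up to 3 or 7 days around the due date. The number of participants attending is also not given.

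Three stronger conclusions are not supported:
- **Bias between arms.** The same cut applies to both arms and nothing in the documents suggests that visit timing differs by arm. The harm is to visit counts and denominators. Efficacy analyses are not involved.
- **Anti-drug antibody results.** SAP 5.7.3 reports them as baseline and post-baseline results, outside SAP 5.6 and with no split by period.
- **Misplaced adverse events.** An event with onset by day 98 stays in the double-blind period if periods are assigned by onset date. SAP 5.6 refers to data collected and does not say which date is used.

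**What to change.** In SAP 5.6, before unblinding, make one of two changes:

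1. Assign the 14-week follow-up visit's laboratory, ECG and vital-sign results to the double-blind period by nominal visit; or
2. Add a fixed visit allowance, in days, to the 14-week cut.

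Keep the cap at the day before the first OLE dose in either case, and apply the same rule to the OLE period's 14-week cut. The first option is cleaner: it needs no assumed window, of which the protocol states none for this visit, and it leaves the adverse-event period as it is. The second would lengthen the adverse-event period by the same number of days unless it is limited to visit-based assessments.

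The cost is one sentence and a small change to the period flag. The downside is that a few visits held slightly later than 14 weeks are counted in the double-blind tables. If the full text of SAP 5.6 or the Data Analysis Plan modules already contains such a rule, it is enough to state it or cross-refer to it in SAP 5.6.
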